Title: Does early platelet rich plasma injection decrease the risk of post-traumatic arthritis in pilon fractures undergoing two-staged open reduction with internal fixation?

Protocol version: 1.3

Protocol date: 08/30/2016

Principal Investigator: [name]

NCT: 02481869

A) Scientific Aims

Specific Aim 1: Determine the effects of a single intra-articular injection of platelet rich plasma (PRP) for mitigating the development of post-traumatic arthritis (PTA) in patients being surgically treated for pilon fractures in one ankle.

Null hypothesis: A single intra-articular injection of platelet rich plasma (PRP) will not be associated with significant improvements in outcome based on patient-reported measures of pain and function, as well as diagnostic imaging findings of PTA in patients being surgically treated for pilon fractures in one ankle.

Specific Aim 2: Assess the discriminatory potential of a synovial fluid biomarker panel for categorizing presence and severity of PTA based on patient-reported outcome measures of pain and function, as well as diagnostic imaging findings in patients being treated for pilon fractures in one ankle.

Null hypothesis: Synovial fluid biomarkers will not have high discriminatory capabilities for categorizing presence and severity of PTA in patients being treated for pilon fractures in one ankle.

B) Background and Significance

Pilon fractures are common and are associated with a 75% chance for symptomatic post-traumatic arthritis (PTA).¹ Although the mechanisms for initiation and progression of PTA after pilon fracture are incompletely understood, articular fracture is known to induce pro-inflammatory cytokines and degradative enzymes, which can result in chondrocyte death, accelerate cartilage degradation, and drive synovitis after injury. These pathologic processes appear to be especially important in the early phases of disease.²⁻⁴ Current treatments for articular fractures are focused on biomechanical issues: anatomic reduction, rigid stability, and limb alignment. These are critical issues to address for optimal healing, early limb use, and joint function. However, the biologic components of articular fracture are likely as, or even more important, with respect to development of PTA. As such, research efforts also need to focus on these important aspects in order to mitigate the development and progression of joint pathology after articular fracture.

In an in vitro study, antioxidant treatment delivered hours after articular cartilage injury was reported to prevent progression of PTA-related pathology.⁵ Using canine models of PTA, our group has noted significant benefits after intra-articular injection of platelet rich plasma (PRP) in decreasing pain, improving limb use, maintaining joint range of motion, and mitigating progression of osteoarthritis. Beneficial results associated with PRP treatment of OA have also been reported in clinical veterinary patients.⁶ Based on this translational evidence in conjunction with the regulatory status and availability of PRP for clinical use in trauma patients, this orthobiologic therapy appears to have strong potential for providing a practical means of mitigating development of PTA in patients suffering ankle fracture. Importantly, we will be able to use a synovial fluid biomarker panel that has been shown to have high discriminatory potential for categorizing presence and severity of OA in dogs⁹, to assess patients for PTA after pilon fracture – which provides critical data regarding disease mechanisms^{7,8} – and treatment monitoring for development and assessment for novel therapeutic strategies for this pervasive problem.

C) Previous Work on the Study

There has been little published work on this particular treatment strategy for post traumatic arthritis of the ankle

D) Methods

With IRB approval and informed consent, patients (n=40) will be included who sustain closed pilon fracture of one ankle and are undergoing initial reduction with spanning external fixation, followed by open reduction with internal fixation (ORIF). Up to 50 patients will be enrolled in order to account for expected attrition in this patient population. Patients will be randomized to one of two treatment groups:

- PRP (n=20): single intra-articular injection of 5 ml of a leukocyte-reduced platelet rich plasma (ACP, Arthrex, Naples, FL) at the time of closed reduction and initial stabilization using ankle-spanning external fixation

- Control (n=20): single intra-articular injection of 5 ml of sterile 0.9% saline at the time of closed reduction and initial stabilization using ankle-spanning external fixation

Study candidates will be identified as they present to the University Hospital emergency room or clinics and will be recruited for enrollment. Informed consent will be obtained as per IRB protocol. The patients will be approached by an orthopedic resident physicians, attending, or study staff to present the current study. Patients will be told of the details of the study and what is required of them if they chose to participate. The patients will be randomized by envelope to one of two groups, the PRP or control group. The patients will be blinded to which treatment they receive. Patients will be treated according to current standard of care, Following initial reduction and placement of ankle-spanning external fixation, synovial fluid will be aseptically obtained via arthrocentesis from both ankles and saved for subsequent biomarker analysis at the Comparative Orthopedic Laboratory. For the injured ankle, the PRP injection will be performed through the same needle used for arthrocentesis. PRP will be isolated from venous blood drawn from a peripheral vein. When appropriate, ORIF will be performed for definitive fracture treatment likely 7-14 days following external fixator placement. Prior to capsulotomy for ORIF, synovial fluid will again be aseptically obtained via arthrocentesis from both ankles and saved for subsequent biomarker analysis.

Follow-up assessments will be performed at 3 weeks, 6 weeks, 12 weeks, 6 months, 12 months, and 18 months after surgery for all patients. Radiographs will be obtained at 6 weeks and each subsequent visit. Patient reported outcomes (PRO) including AOFAS, SF 12 and VAS for pain and level of function will be recorded at all follow-up assessments starting at 3 weeks. At 18 months, MRI of the affected ankle will be performed and used for whole-joint assessment of OA.¹⁰

Number of patients per group was determined from a pre-study power analysis using previously published data on prevalence of PTA after pilon fracture – the assumption being that a 10% reduction in percentage of patients experiencing symptomatic PTA would be clinically significant. Patients and all patient evaluators will be kept blinded to treatment until all data are collected and analyzed by the co-investigator responsible for

all data analyses. For data analysis, PTA presence will be defined based on a diagnosis of OA, or findings consistent with OA, reported for either imaging modality at any assessment time point. PTA severity will be determined from whole-joint MRI scoring and patient reported outcomes at 18 months after surgery and categorized as mild, moderate or severe. To test the first hypothesis, we will compare treatment groups for statistically significant ($p < 0.05$) differences in proportions with PTA, proportions within each severity category, and PRO scores using Fisher's exact tests, t-Tests, and rank sum tests. To test the second hypothesis, we will perform receiver operator characteristic curve analyses to determine the discriminatory capabilities (area under the curve (AUC)) of the panel for distinguishing the presence and severity of PTA. The injured ankle will be compared to the normal, contralateral ankle and $AUC > 0.8$ will be considered to represent high and clinically useful discriminatory capability. In addition, patient age, gender, BMI, tobacco use, and co-morbidities, as well as the CT scan injury severity score¹¹ will be assessed as variables for predicting likelihood of presence and severity of PTA using Fisher's exact test and odd's ratios.

Based on its mechanisms of action and preliminary data, we expect to reject our null hypotheses and show that a single injection of PRP is associated with significant improvements in outcomes. We also expect that our synovial fluid OA biomarker panel will have high discriminatory capabilities for categorizing presence and severity of PTA in patients being treated for pilon fractures in one ankle.

Subject Selection

Inclusion criteria:

- Patients with closed unilateral pilon fractures
- Patients undergoing staged pilon procedures with an external fixator index procedure

Exclusion criteria:

- Patients who are younger than 18 years of age
- Open pilon fracture
- Patients with contralateral lower extremity injury
- Patients unable to comply with the follow-up appointments
- Patients who had previous ankle injury to the currently injured ankle
- Patients who are pregnant
- Prisoners

E) Re-consent of previously incompetent subjects

Subjects who are consented while in an incompetent state will be approached after the procedure if and when they become competent. During the re-consent process, the subject will again be informed of the study details and be given as much time as needed to make their decision to continue enrollment in the study.

F) Quality Assurance of Data Collection:

Patient confidentiality will be maintained by adherence to the rules of HIPAA and the University of Missouri IRB. All patients will have a de-identified Patient Study ID

number and the data will be maintained in a secured environment within the Department of Orthopaedic Surgery. Additionally, copies of study documents will be maintained in a secured location in a locked suite in the Department of Orthopaedic Surgery, with access granted only to the designated research personnel.

References

2. Martin JA, Buckwalter JA: Post-traumatic osteoarthritis: The role of stress induced chondrocyte damage. Biorheology 2006; 43(3-4):517-521.
6. Franklin SP and Cook JL. Prospective trial of autologous conditioned plasma versus hyaluronan plus corticosteroid for elbow osteoarthritis in dogs. Can Vet J 2013;54:881-884.

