## **Data Analysis**

For data analysis, PTA presence will be defined based on a diagnosis of OA, or findings consistent with OA, reported for either imaging modality at any assessment time point. PTA severity will be determined from whole-joint MRI scoring and patient reported outcomes at 18 months after surgery and categorized as mild, moderate or severe. To test the first hypothesis, we will compare treatment groups for statistically significant ( $p < 0.05$ ) differences in proportions with PTA, proportions within each severity category, and PRO scores using Fisher's exact tests, t-Tests, and rank sum tests. To test the second hypothesis, we will perform receiver operator characteristic curve analyses to determine the discriminatory capabilities (area under the curve (AUC)) of the panel for distinguishing the presence and severity of PTA. The injured ankle will be compared to the normal, contralateral ankle and  $AUC > 0.8$  will be considered to represent high and clinically useful discriminatory capability. In addition, patient age, gender, BMI, tobacco use, and co-morbidities, as well as the pre-operative CT scan injury severity score will be assessed as variables for predicting likelihood of presence and severity of PTA using Fisher's exact test and odd's ratios.

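### Aim 2 says the fluid panel categorizes PTA, but both draws precede every PTA assessment: at most prediction can be shown, and the planned ROC does not test that

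*Protocol*

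**What the plan says.** **The aim.** Protocol A) Scientific Aims sets Aim 2 as to "Assess the discriminatory potential of a synovial fluid biomarker panel for categorizing presence and severity of PTA", judged by patient-reported outcomes and imaging. The null uses the same terms: "Synovial fluid biomarkers will not have high discriminatory capabilities for categorizing presence and severity of PTA". The expectation that closes the analysis text in Protocol D) Methods repeats them, and SAP Data Analysis speaks of distinguishing PTA presence and severity. Both documents use the language of prediction for patient characteristics and the CT severity score, but never for the panel.

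**The background.** Protocol B) says "we will be able to use a synovial fluid biomarker panel that has been shown to have high discriminatory potential for categorizing presence and severity"; the disease meant there is canine OA. It goes on to link the panel to "treatment monitoring for development and assessment for novel therapeutic strategies for this pervasive problem".

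**The sampling.** Protocol D) Methods lists two draws. First: "Following initial reduction and placement of ankle-spanning external fixation, synovial fluid will be aseptically obtained via arthrocentesis from both ankles". For the injured ankle, "the PRP injection will be performed through the same needle used for arthrocentesis", so this draw is pre-treatment. Second: "Prior to capsulotomy for ORIF, synovial fluid will again be aseptically obtained via arthrocentesis from both ankles and saved for subsequent biomarker analysis". ORIF is expected 7-14 days after the fixator is placed. No fluid is listed at any of the six follow-up visits.

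**The reference standard.** PTA presence is a finding of OA on either imaging modality at any time in follow-up. Follow-up radiographs start at 6 weeks, and MRI of the affected ankle is at 18 months. For severity, "PTA severity will be determined from whole-joint MRI scoring and patient reported outcomes at 18 months after surgery".

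**The analysis.** The ROC text compares the injured with the uninjured contralateral ankle and takes AUC > 0.8 as the mark of useful discrimination. It does not say which draw is used.

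**The concern.** A claim that a panel categorizes disease needs the marker and the disease status to be measured at about the same time. Here the marker describes a joint in its first days or weeks after fracture, and the status is read weeks to many months later. A high AUC would nevertheless be reported as showing that the panel categorizes PTA presence and severity. A low AUC would be reported as failure to do so, although no fluid was taken when PTA was assessed. This concerns the conclusion drawn for one of the trial's two specific aims.

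The contralateral comparator adds to the problem. Correcting the timing language to prediction is not enough if the ROC still separates fractured from uninjured ankles.

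**Working it through.** The plan states no figure for this point, so there is nothing to reproduce. The check is a timeline, followed by two illustrations.

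**1. Timeline.** Inputs from Protocol D) Methods: g = days from external fixation to ORIF, likely 7 to 14; first patient-reported outcomes at 3 weeks = 21 days; first follow-up radiograph at 6 weeks = 42 days; MRI and severity at 18 months = 18 × 30.4375 ≈ 548 days. Follow-up is timed from surgery, without saying which procedure, so both readings are shown.

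| Interval (days) | Counted from ORIF | Counted from external fixation |
|---|---|---|
| Draw 2 to first patient-reported outcome | 21 | 21 − g = 7 to 14 |
| Draw 2 to first radiograph | 42 | 42 − g = 28 to 35 |
| Draw 2 to severity grade | about 548 | 548 − g = about 534 to 541 |
| Draw 1 to first radiograph | 42 + g = 49 to 56 | 42 |
| Draw 1 to severity grade | 548 + g = about 555 to 562 | about 548 |

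No draw coincides with any assessment that defines PTA on either reading. The 7-14 days are an expectation, not a limit. On the external-fixation reading, ORIF would have to be delayed to 42 days before draw 2 reached the first radiograph.

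**2. What the planned ROC measures.** For two normal distributions with equal variance whose means differ by d standard deviations, AUC = Φ(d/√2). The documents give no d, so these values are assumptions for the difference between injured and contralateral ankles:

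- d = 1.2: Φ(0.849) = 0.80
- d = 1.5: Φ(1.061) = 0.86
- d = 2.0: Φ(1.414) = 0.92

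Suppose the panel carries no information on later PTA. The AUC for PTA versus no PTA among injured ankles is then 0.50, yet the planned comparison passes 0.8 once d reaches about 1.2. It can be met by detecting the acute fracture alone. In addition, MRI is planned only for the affected ankle, so the contralateral ankle has no MRI reference standard.

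**3. Precision of an ROC among injured ankles.** Assume that all 40 planned patients are analysed and that 65-75% develop PTA (26 to 30 cases). The 75% in Protocol B) is for symptomatic PTA; applying it to imaging-defined PTA is an assumption. The Hanley-McNeil formula, with A = 0.80, Q1 = A/(2 − A) = 0.667 and Q2 = 2A²/(1 + A) = 0.711, gives for 30 versus 10:

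SE = √{[0.16 + 29(0.667 − 0.64) + 9(0.711 − 0.64)]/300} = 0.072

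The 95% interval is 0.80 ± 1.96 × 0.072, or 0.66 to 0.94. For 26 versus 14, SE = 0.069 and the interval is again 0.66 to 0.94.

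**The case against.** The strongest reply is that discrimination and ROC analysis apply to prognostic markers as well as diagnostic ones. Neither document calls the panel a diagnostic test. Aim 2 names its reference outcomes, which are scheduled at follow-up, and the draw times are stated openly. Categorizing patients by later PTA status is therefore a possible reading. This stands as a reason to treat the repair as modest. It does not remove the problem, because no sentence says prediction for the panel and the planned comparator does not fit that reading.

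Three stronger inferences are tempting, and the documents do not support them:

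- **That a high AUC would at least show prediction.** Under the planned comparison it would show only that a fractured ankle differs from an uninjured one.
- **That the trial sets out to prove treatment monitoring.** The phrase occurs only in Background; no aim, null hypothesis or analysis uses it. The two draws do allow a short-term comparison before and after the injection, which is much narrower than monitoring PTA.
- **That the panel is never tested in a joint with PTA.** The protocol describes fracture as starting the degradative process and stresses the early phases of disease, and it gives no onset time for PTA. What can be said is that PTA is not assessed when fluid is drawn.

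**Conclusion.** The point holds in this form: both draws precede every assessment that defines PTA, so the data can support at most a claim that early fluid predicts later PTA, and the planned ROC does not test that claim. The last draw precedes the first follow-up radiograph by about 6 weeks (from ORIF) or 4-5 weeks (from external fixation), and the severity grade by about 18 months.

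The direction does not depend on which procedure starts the clock. The exact gaps do, and they also rest on ORIF falling within the expected 7-14 days. The conclusion assumes that no follow-up fluid sampling is planned outside the text available here; part of the SAP was not available. The AUC values rest on assumed side differences and the interval on assumed PTA rates. Aim 1 and the sample size are not affected.

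**What to change.** 1. Reword Aim 2, its null hypothesis, the closing expectation in Protocol D) Methods and the SAP Data Analysis sentence as prediction, from early synovial fluid, of PTA presence during follow-up and PTA severity at 18 months. Keep the existing definition of presence, which counts imaging findings at any follow-up time; moving it to 18 months would change the reference standard.
2. Run the ROC among injured ankles, comparing those with and without later PTA, and by severity category.
3. Report each draw separately and by name. Make the pre-injection draw the main analysis. The second draw follows PRP or saline and may reflect treatment, so adjust for or stratify by arm there.
4. Interpret AUC > 0.8 as predictive discrimination only, and do not conclude that the panel diagnoses or monitors PTA.

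The cost is new wording and a respecified ROC on samples already planned, with no extra arthrocentesis. The downside is a narrower claim and fewer ankles: with 40 patients, 40 injured ankles instead of 80 ankles from both sides. The interval around an AUC of 0.80 would run from about 0.66 to 0.94 under the assumptions above, and it should be reported beside the point estimate.

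### Injury severity is named as a predictor of PTA, yet the Aim 1 comparison is unadjusted and no stratification is stated, so precision is given up in arms of 20

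*Protocol*

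**What the plan says.** Protocol section D (Methods) gives the whole of the allocation procedure: "The patients will be randomized by envelope to one of two groups, the PRP or control group". The arms are set out as "PRP (n=20): single intra-articular injection of 5 ml" and "Control (n=20): single intra-articular injection of 5 ml of sterile 0.9% saline", with this allowance for loss: "Up to 50 patients will be enrolled in order to account for expected attrition in this patient population". Neither the protocol nor the available SAP text describes how the sequence is generated, whether it is blocked or stratified, what the envelopes are like, or who prepares, keeps and opens them.

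For Aim 1, the protocol's Methods and the SAP's Data Analysis section name the same tests: Fisher's exact, t and rank sum, at a 0.05 threshold. Neither names a covariate or stratum for the arm comparison. Severity appears only in a separate analysis of what predicts PTA, where the SAP lists the "pre-operative CT scan injury severity score" beside age, gender, BMI, tobacco use and co-morbidities. The reference given for the score is a study of CT-based fracture severity metrics and PTA risk.

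**The concern.** The plan collects a baseline measure because it is expected to predict the outcome, and then leaves that measure out of the comparison it could sharpen. In the available text, severity is controlled neither by design (strata) nor by analysis (adjustment). Arms of 20 can differ noticeably in severity by chance. If severity drives PTA as the plan supposes, part of the scatter in the observed arm difference is then avoidable.

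At stake are the precision and readability of a small trial. If the arms turned out unequal in severity, an unadjusted result would be hard to interpret, and an adjustment chosen after seeing the data would carry little weight.

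**Working it through.** **The plan's own figure.** The plan gives no figure for imbalance or for the prognostic strength of severity. Its only related figure is 20 per arm, attributed to a power analysis for a 10% reduction from published PTA prevalence (75% in the protocol's Background). That does not reproduce. For 75% v 65%, two-sided 0.05 and 80% power, n = [1.96·√(2·0.70·0.30) + 0.84·√(0.75·0.25 + 0.65·0.35)]² / 0.10² = 329 per arm. If the reduction is relative (75% v 67.5%), 571 are needed. This is a separate problem, and the present point does not depend on it. The enrolment figure is consistent with 20% attrition: 40/(1 − 0.20) = 50.

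**Inputs.**
- From the documents: 20 per arm; 75% control risk; a 10-point reduction (read as absolute, giving 65%).
- Assumed, because the documents give no value: severe-fracture prevalence p of 0.3 to 0.5; a PTA risk gap g between severity classes of 10, 20 or 30 points.

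**Step 1: how often the arms differ in severity.** The severe counts in the two arms are independent Binomial(20, p). A gap of 20 points is 4 patients.

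| p | P(gap ≥ 20 points), 20 per arm | Same, 25 per arm |
|---|---|---|
| 0.3 | 23% | 16% |
| 0.4 | 26% | 19% |
| 0.5 | 27% | 20% |

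For a continuous score, the standardised difference between arms has SE √(2/20) = 0.32, and a difference of 0.5 SD or more occurs in 11% of trials.

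**Step 2: what this does to the PTA difference.** The SD of the severity gap at p = 0.5 is √(2·0.5·0.5/20) = 15.8 points. The SE of the PTA difference is √(0.75·0.25/20 + 0.65·0.35/20) = 14.4 points. The share of variance due to severity imbalance is (g × 15.8/14.4)², with g as a proportion:
- g = 0.10: (1.58/14.4)² = 1%
- g = 0.20: (3.16/14.4)² = 5%
- g = 0.30: (4.74/14.4)² = 11%

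At p = 0.3 the SD of the gap is 14.5 points, and the shares are 1%, 4% and 9%.

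In a single trial with a 20-point gap and g = 0.30, the PTA difference moves by 0.20 × 30 = 6 points. That should be read beside the 14.4-point SE, which already contains this variation, and not only beside the 10-point target.

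**Step 3: what analysing by severity gains.** Removing the 11% share takes the SE from 14.4 to 14.4 × √(1 − 0.108) = 13.6 points. By normal approximation, power for 75% v 65% goes from 10.7% to 11.4%.

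A simulation of exact tests with 20 per arm, half the fractures severe and g = 0.30 gave:
- Size of the severity-stratified exact test: under 3%.
- Power for 75% v 65%: about 5.5% with Fisher's test, about 7% stratified. Direct enumeration of Fisher's test gives 6%.
- Power for 75% v 35%: about 62% with Fisher's test, about 72% stratified.

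Some of that gain arises because the stratified test is less discrete, and so less conservative, than Fisher's test on 20 v 20. The documents give no correlation between severity and the patient-reported scores, so no figure is offered for those outcomes.

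**The case against.** **Chance imbalance is not bias.** Under randomisation the unadjusted tests hold their size, and the estimate is right on average. The ordinary standard error already counts the imbalance. This stands in full, and it is why the point concerns precision only.

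**The size rests on assumed inputs.** This also stands. With a 10-point risk gap the loss is about 1% of the variance, which is negligible. The case is material only if severity is a strong predictor, as the plan itself expects.

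**Absence of strata is read from silence.** This is fair, since part of the SAP was not available for this review. But strata would have to be stated to be followed, and the Methods section where allocation is described does not mention any.

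**Stratified envelopes have limits.** With blocks of 4 in two strata, the severe share could differ by at most about 10 points at 20 per arm. If 50 are randomised and 10 lost at random, the SD of the gap is about 7.7 points and gaps of 10 points or more occur in about 24% of trials. Fixed blocks also raise predictability: someone who knew all past allocations could guess 71% correctly with blocks of 4, against 50% under simple randomisation. Both points stand. They favour making adjustment the main remedy and, if blocks are used, varying their size.

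**A stronger reading that the documents do not support.** The protocol says "The patients will be approached by an orthopedic resident physicians, attending, or study staff to present the current study", and one exclusion calls for judgement: "Patients unable to comply with the follow-up appointments". A reader might infer that recruiters handle the envelopes, can foresee the next allocation, and can let it affect who is enrolled. Nothing says so. Study staff may also recruit, custody of the envelopes is unstated, and consent is described before randomisation. With sealed opaque envelopes and simple randomisation the next allocation cannot be foreseen. Concealment and custody are unreported, which is a gap in description and not evidence of selection bias.

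**Conclusion.** The point holds as one about efficiency. The plan names injury severity as a predictor of PTA but uses it neither in the Aim 1 comparison nor, in the available text, in the allocation. The planned analysis is valid and unbiased on average. It gives up roughly 1% to 11% of the variance of the arm difference, depending on an assumed risk gap of 10 to 30 points with about half the fractures severe. The benefit of adjusting is real for a large effect and slight for the 10-point effect that the plan calls clinically significant. It would be wrong to conclude that the result will be biased, or that stratification would make the trial adequately powered.

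**What to change.** 1. **Analysis, for all patients.** State in the protocol and SAP that Aim 1 is analysed by severity, using the pre-operative CT score already planned. For PTA presence, use a stratified exact test on a split of the score fixed before unblinding. For patient-reported scores, include the score as a covariate. The score should be read without knowledge of allocation, because the documents do not say whether the CT precedes the external fixator procedure, when the injection is given.

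2. **Allocation, for patients not yet randomised.** Where a severity class is available before the external fixator procedure, stratify the envelopes by it. Use sequentially numbered, sealed, opaque envelopes in randomly varying blocks, prepared by existing staff who do not recruit, and analyse by that stratum. State who keeps and opens the envelopes, and that eligibility and consent are recorded first; this also closes the gap in description.

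**Cost.** A few sentences of protocol and SAP text and, for the second step, a new list and envelope set. Severity must be recorded for every patient and a cut-off chosen in advance. The first step needs no new measurement beyond the planned score. The gain is modest, and the shortfall in power for a 10-point effect remains.
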